4.2 Inclusion Criteria

Subjects must meet all of the following criteria to be enrolled in this study:

- Aged 21 years or older and below 100 years of age.
- Signed written informed consent and willingness to comply with protocol requirements.
 - Histologically confirmed diagnosis of metastatic prostate cancer
- Staging imaging exam confirming metastatic disease, e.g. total body MRI, or CT chest/abdomen/pelvis, 99mTc bone scan, NaF PET.

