11.2.5 Record Retention

Essential documents are those documents that individually and collectively permit evaluation of the study and quality of the data produced. After completion of the study, all documents and data relating to the study will be kept in an orderly manner by the Investigator in a secure study file. Essential documents should be retained for 2 years after the final marketing approval in an ICH region or for at least 2 years since the discontinuation of clinical development of the IP. In addition, all subjects medical records and other source documentation will be kept for the maximum time permitted by the hospital, institution, or medical practice.

12. Statistical Considerations

Up to 30 patients will undergo a dynamic whole-body scan with ^{68}Ga -PSMA_{Gen} and later ^{68}Ga -PSMA_{cyc} with a maximum time of 2 days and a minimum time of 6 h between the two injections. All 22 patients will receive ^{68}Ga -PSMA_{Gen} at a specific activity of 1-2 Ci/ μmol , the typical specific activity used in clinical trials with ^{68}Ga -PSMA. We expect the ^{68}Ga -PSMA_{cyc} to be delivered and injected at a specific activity of 0.1- 2.0 Ci/ μmol given the rigors of delivery. We will accept doses in this range as the prior small animal imaging was designed to understand the affect of specific activity over a 20X range.

For a power of 80% a calculation of the sample size needed to test odds ratio (equality test) was performed. A sample size of 22 would give a power percentage of 18.47 with a type 1 error of 5%. This power percentage is sufficient in providing confidence that the findings will reflect a true effect. The median statistical power of studies in the neurosciences is between ~8% and ~31%. We will not and should not be focusing on p-values but rather the estimates of the effect size with its confidence intervals.

Estimating repeatabilities using a mixed effects model framework has proven to be powerful, the repeatability (r) is calculated as the variance among group means (group-level variance) over the sum of group-level and data-level (residual) variance (v). A Pearson's correlation coefficient will demonstrate also present the repeatability of results. Intraclass correlation values for both groups will be calculated to test if the groups differ in repeatability. These collection of tests(functions) for estimating repeatability of measurements with a single grouping factor are all performed in R statistical software.

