To quantify the agreement between the two scans, we will use the repeated measures correlation coefficient to account for multiple observations per subject. We will calculate the repeated measures correlation-coefficient for the SUVmax and SUVmean for reference regions as well as regions suspicious for metastatic disease. We will measure SUVmean and SUVmax of the same Regions of Interest (ROI) in both scans using the PET analysis software we use in our clinical practice. The two scans will be retrieved and the exact same ROIs will be drawn at the same time for the two scans (software offers a copy-paste function so that no discrepancies exist between the two measurements). The SUVmean and SUVmax obtained from both scans for each Region of Interest will then be analyzed to determine the within-subject coefficient of variation value as measured by the Bland Altman analysis. If the agreement between the two scans lies within an acceptable rate (which we consider 30% based on previously published data), we will consider the two methods equivalent.

Also, as aforementioned the Bland-Altman Test presents proof of repeatability analysis.

13. Adverse Event Reporting Requirements

Adverse event (AE) monitoring and reporting is a routine part of every clinical trial. The investigator will be required to provide appropriate information concerning any findings that suggest significant hazards, contraindications, side effects, or precautions pertinent to the safe use of the drug or device under investigation. Safety will be monitored by evaluation of adverse events reported by subjects or observed by investigators or research staff, as well as by other investigations such as clinical laboratory tests, x-rays, electrocardiographs, etc.

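### For suspicious regions, the repeated measures correlation gives no weight to patients with a single region, so it cannot register disagreement between the two products in those patients

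*Combined protocol and SAP*

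**What the plan says.** Section 12 (Statistical Considerations) names the statistic and its purpose: "To quantify the agreement between the two scans, we will use the repeated measures correlation coefficient to account for multiple observations per subject". It is to be calculated "for the SUVmax and SUVmean for reference regions as well as regions suspicious for metastatic disease". The text does not say outright that the two classes of region are analysed separately, though that is the natural reading. It gives no formula or software function for this coefficient, no threshold for it, and no rule for a patient with one region.

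The data are paired by region: "We will measure SUVmean and SUVmax of the same Regions of Interest (ROI) in both scans". One region therefore yields one cyclotron/generator pair.

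On eligibility, Section 4.2 asks for "Staging imaging exam confirming metastatic disease" and for histological confirmation. It sets no minimum number of lesions.

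Section 12 and the Endpoints entry of the Protocol Summary also plan a Bland-Altman within-subject CV on each region. Section 12 follows it with a 30% criterion for calling the two methods equivalent. The Endpoints entry does not mention the correlation. Section 12 further lists Pearson and intraclass correlations.

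**The concern.** The plan chooses this coefficient because patients may contribute several regions. The coefficient handles that by removing each patient's own level and looking only at how regions vary together within a patient. A patient with one suspicious region has no within-patient variation to offer. Such a patient is eligible, is injected and scanned twice, and supplies a valid lesion pair, yet has no influence on the figure named to quantify lesion agreement.

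The loss is silent. Neither the coefficient nor its interval shows how many patients contributed. If the cyclotron product showed the only lesion of such a patient poorly, the coefficient would be the same as if the two scans had matched exactly. Section 12 says that interpretation should rest on effect estimates and confidence intervals, and for this statistic both omit these patients.

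**Working it through.** **Inputs.** Paired design, one pair per region, coefficient applied to suspicious regions (Section 12). No minimum lesion count (Section 4.2). Number of patients: Section 12 gives both "Up to 30 patients will undergo a dynamic whole-body scan" and "All 22 patients will receive", so 22 and 30 were both used. Lesion counts, SUV values and measurement error are not in the documents. Those used below are assumptions.

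**The plan's own figure.** The only stated design figure is "A sample size of 22 would give a power percentage of 18.47 with a type 1 error of 5" percent, for an odds-ratio test. It cannot be reproduced, because no odds ratio or reference proportion is given. Nothing below depends on it.

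**Algebra.** For patient i and lesion j, let x be the generator SUV and y the cyclotron SUV, each centred on the patient's own mean:

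r = Σ(x_ij − x̄_i)(y_ij − ȳ_i) / √[Σ(x_ij − x̄_i)² · Σ(y_ij − ȳ_i)²]

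df = (total pairs) − (patients) − 1

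With one lesion, x_i1 = x̄_i and y_i1 = ȳ_i. Both centred values are 0, and the patient adds 0 to all three sums. The patient adds one pair and one patient to df, a net change of 0. A patient with k lesions adds k − 1.

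**Worked example (invented values).**
- Patient A: pairs (4, 5), (8, 8), (12, 11). Patient B: pairs (5, 5), (9, 10). Patient C: one pair, (6, 6).
- Centred x: −4, 0, 4; −2, 2; 0. Centred y: −3, 0, 3; −2.5, 2.5; 0.
- Cross-product sum 34, Σx² = 40, Σy² = 30.5, so r = 34/√(40 × 30.5) = 0.973, with df = 6 − 3 − 1 = 2.
- Change C's pair to (6, 0): C's centred values are still 0 and 0, so r = 0.973 and df = 2, as before.

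**Simulation.** 22 or 30 patients, about 10% to 50% with one lesion and the rest with four, and about 10% error per scan. The second-scan values of the one-lesion patients were multiplied by 0.1, multiplied by 10, or randomised. The coefficient was computed from centred values and also by analysis of covariance with patient as a factor. The two agreed, and the coefficient was unchanged to six decimals in all eight settings. Two of them:

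| Patients (one-lesion) | df | r, unaltered | r, all alterations | CV, unaltered | CV, ×0.1 | CV, ×10 |
|---|---|---|---|---|---|---|
| 22 (7) | 44 | 0.958566 | 0.958566 | 0.104 | 0.587 | 0.568 |
| 30 (9) | 62 | 0.966183 | 0.966183 | 0.101 | 0.528 | 0.577 |

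Check of df: (15 × 4 + 7) − 22 − 1 = 44, and without the one-lesion patients 60 − 15 − 1 = 44. Likewise (21 × 4 + 9) − 30 − 1 = 62 and 84 − 21 − 1 = 62.

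**If the region classes were pooled.** With three assumed reference regions per patient in the same coefficient, the single lesion is no longer alone. In the 22-patient setting with 7 one-lesion patients, r moved from 0.980 to 0.935 (×0.1) or 0.462 (×10).

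**How far the planned CV makes up for it.** Assume 8 patients with one lesion and 22 with eight, 10% error per scan, and the cyclotron SUV of the one-lesion patients multiplied by 0.25.
- Within-pair log variance of an unaffected lesion: 0.01. Of an affected lesion: 0.01 + (ln 4)²/2 = 0.971.
- Pooled over lesions: (8 × 0.971 + 176 × 0.01)/184 = 0.0518, root 0.228, a CV of about 23%.
- Each patient weighted equally: (8 × 0.971 + 22 × 0.01)/30 = 0.266, root 0.516, a CV of about 52% (55% with the lognormal conversion √(e^0.266 − 1)). Similar simulated data with varying lesion counts gave 50% to 57%.

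The CV therefore responds, but pooling over lesions dilutes the response.

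**The case against.** The strongest reply is that this coefficient does not decide equivalence. The primary endpoint is the Bland-Altman within-subject CV on each region, the 30% criterion comes directly after it in Section 12, and the correlation has no threshold. One-lesion patients stay in the CV. Because the same region is copied to both scans, a faint sole lesion would still appear there as an extreme pair. This stands. A reader might infer that whole patients leave the agreement analysis, or that the equivalence decision ignores them. The documents do not support either inference. The remaining caution is the dilution shown above: in that scenario a CV pooled over lesions is about 23%, below 30%, although 8 of 30 patients disagree fourfold.

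A second reply is that the property is conditional. It needs the standard within-patient coefficient and separate calculation for suspicious regions. The plan states neither. A weighted correlation of patient means, or one coefficient pooled over both classes, would use these patients. This also stands, and it is a reason to say which is meant.

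A third reply is that the practical size is unknown. That is correct: no lesion counts are given, and any share of one-lesion patients is an assumption. The zero weight itself does not depend on the share.

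Finally, the coefficient measures association rather than agreement in any patient. Halving every second-scan value among multi-lesion patients left it at 0.936. That wider weakness shares the main remedy. The silent omission of patients needs one further step, which is to report who contributes.

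**Conclusion.** The point holds for this coefficient. In its standard form on suspicious regions alone, patients with one suspicious region have exactly zero influence on the estimate and its confidence interval, however far their two scans differ. The result therefore describes only patients with two or more suspicious regions, each weighted by k − 1. This is an algebraic property, and the simulations only illustrate it.

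It rests on two readings of Section 12: the usual definition of the coefficient, and separate analysis of the two region classes. How many patients are affected cannot be determined from the documents. The equivalence decision, on the natural reading of the 30% criterion, does not exclude these patients, but it may underweight them if the CV is pooled over lesions. The plan should be corrected, because following it as written gives a lesion agreement figure that omits eligible, scanned patients without notice.

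**What to change.** In Section 12:

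1. For suspicious regions, make the agreement measure a mixed model of ln(SUV cyclotron / SUV generator) per lesion with a random patient effect, for SUVmax and SUVmean. Report the mean ratio and the limits of agreement, both with confidence intervals, taking the limits from the between-patient and within-patient variance together. Every patient with a measured lesion then contributes.
2. State that the 30% criterion applies to the Bland-Altman within-subject CV and not to the correlation, and say whether that CV is pooled over lesions or weighted by patient.
3. If the correlation is kept, label it descriptive, say whether reference and suspicious regions are analysed separately, and report how many patients contribute to it. List the pairs from one-lesion patients.

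The cost is SAP wording and a few lines of R, which the plan already uses. No new data, scans or patients are needed.

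### The planned repeated-measures correlation adjusts for patient but not organ, so if the reference regions differ in uptake it overstates how well the two scans agree

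*Combined protocol and SAP*

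**What the plan says.** Section 12 (Statistical Considerations) introduces the statistic as the way to quantify agreement between the two scans: "we will use the repeated measures correlation coefficient to account for multiple observations per subject". It is applied "for the SUVmax and SUVmean for reference regions as well as regions suspicious for metastatic disease". The data are described as follows: "We will measure SUVmean and SUVmax of the same Regions of Interest (ROI) in both scans".

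Section 12 gives no organ term, no stratification by organ and no log transform for this coefficient. The reference regions are not listed. The repeatability tools described just before it are for "estimating repeatability of measurements with a single grouping factor are all performed in R statistical software".

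The same section then sends the SUVs from each region to a within-subject CV and Bland-Altman analysis, and calls the methods equivalent if agreement lies within 30%. The endpoint paragraph of the Protocol Summary names only the within-subject CV by Bland-Altman analysis. No threshold is set for the correlation, and Section 12 says that estimates and confidence intervals, not p-values, will be the focus.

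**The concern.** Repeated-measures correlation fits one intercept per patient and one common slope. That suits repeats within a patient that are exchangeable. Here the repeats are different organs, and the same organs recur in every patient. Once patient means are removed, much of what is left in the reference regions may be the stable difference between high-uptake and low-uptake organs, which any two PSMA scans would share.

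The coefficient would then be high partly for a reason unrelated to whether one patient's two scans match. The plan names this statistic as its measure of agreement, and it would be reported beside the equivalence conclusion. A reader could take a value near 0.9 as strong support for interchangeability when organ contrast alone can produce it. This is separate from the fact that a correlation ignores a proportional difference between products: the calculations below contain no product difference.

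**Working it through.** **Plan's own figure.** The plan gives none for this coefficient. Its only power figure, 18.47% at N = 22, is for an odds-ratio test whose odds ratio and proportions are not stated. It cannot be reproduced and plays no part here.

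**Step 1: must regions be pooled?** With N patients and k regions, one pair each, the coefficient has N(k − 1) − 1 degrees of freedom. For a single organ, k = 1 gives N × 0 − 1 = −1, so it cannot be computed. With six organs and N = 30 it has 30 × 5 − 1 = 149. Pooling is unavoidable.

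**Step 2: inputs.**
- From Section 2.4.1, Table 1 (rad/mCi): kidneys 0.969, spleen 0.165, liver 0.114, heart wall 0.0403, muscle 0.0389, red marrow 0.0340. Kidney/muscle = 24.9; liver/muscle = 2.9.
- From Section 12: N = 22 or 30.
- Assumed: absorbed dose stands in for relative SUV; SUVs are lognormal; between-patient CV per organ is 30% to 50%; the choice of organs is illustrative.

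**Step 3: scans from unrelated patients.** Let μ be the organ means and c the between-patient CV. After patient means are removed:
- organ part: A = Σμ² − (Σμ)²/k
- patient-specific part: B = (1 − 1/k) c² Σμ²
- only A is shared by the two scans, so r ≈ A/(A + B).

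Six organs: Σμ = 1.3612, Σμ² = 0.98348, A = 0.98348 − 1.3612²/6 = 0.67466. At c = 30%, B = (5/6)(0.09)(0.98348) = 0.07376 and r ≈ 0.67466/0.74842 = 0.90. At c = 50%, B = 0.20489 and r ≈ 0.77.

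| Reference regions | A | Σμ² | r approx., c = 30% / 50% | Simulated median, N = 30 |
|---|---|---|---|---|
| All six | 0.67466 | 0.98348 | 0.90 / 0.77 | 0.91 / 0.79 |
| Without kidney | 0.01375 | 0.04451 | 0.81 / 0.61 | 0.82 / 0.62 |
| Liver, heart wall, muscle | 0.00369 | 0.01613 | 0.79 / 0.58 | 0.80 / 0.60 |
| Heart wall, muscle, marrow | 0.00002 | 0.00429 | 0.08 / 0.03 | 0.08 / 0.03 |

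N = 22 gives the same values to within about 0.01. Using log SUV does not cure it (six organs: 0.95 / 0.88). Removing organ means as well as patient means from log SUV brings the median to about 0.00 in every set.

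**Step 4: genuinely paired scans.** With between-patient CV b and within-subject CV w,

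r ≈ [A + (1 − 1/k) b² Σμ²] / [A + (1 − 1/k){(1 + b²)(1 + w²) − 1} Σμ²].

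Six organs, b = 30%, w = 40%: (0.67466 + 0.07376)/(0.67466 + 0.21669) = 0.84; simulated 0.85. At b = 50%: 0.84; simulated 0.86. The log-scale correlation within one organ is ln(1 + b²)/[ln(1 + b²) + ln(1 + w²)], which is 0.37 at b = 30% and 0.60 at b = 50%.

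As scan error grows (b = 30%, six organs, N = 30):

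| Within-subject CV | 10% | 30% | 40% | 60% | 80% |
|---|---|---|---|---|---|
| Pooled coefficient (simulated) | 0.99 | 0.91 | 0.85 | 0.73 | 0.62 |
| Within-organ correlation (formula) | 0.90 | 0.50 | 0.37 | 0.22 | 0.15 |

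**The case against.** **The decision rests elsewhere.** The Protocol Summary endpoint names only the within-subject CV, the 30% rule follows the Bland-Altman sentence, and the correlation has no threshold. A reader might infer that the inflated coefficient could produce a false equivalence verdict. The documents do not support that: read as a CV limit, the 30% rule would itself reject the 40% example. What remains is that Section 12 presents the correlation as its measure of agreement, and the rule refers to agreement without tying the word to one statistic.

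**The coefficient does respond to scan error.** This stands. A reader might infer that it says nothing about whether the scans match, or that with six organs every value must fall between 0.91 and 0.99. Neither is right. It falls steadily with error and is 0.85 at a within-subject CV of 40%, below the value for unrelated patients. Unrelated scans at a between-patient CV of 30% also differ within a pair by a CV of 30%, exactly the plan's limit, so 0.91 is not the coefficient's floor. The fault is compression and dependence on organ mix.

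**No test of zero correlation is planned.** This also stands, so how often such a test would reject is beside the point. The estimate itself is the problem.

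**The reference regions are not named, and Table 1 gives dose, not SUV.** This makes the point conditional. With near-equal regions the inflation almost vanishes.

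**Some of the remedy may already be planned.** The within-subject CV analysis can be read as region by region. That helps, but it does not change how the correlation is computed. Organ-by-organ correlation is no clean substitute either: at the same 40% error it moves from 0.37 to 0.60 with between-patient spread alone.

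**Conclusion.** The point holds conditionally. That regions must be pooled follows from the design. If the reference regions differ in uptake by about 3-fold or more, organ contrast alone gives a coefficient of 0.91 to 0.79 (six organs), 0.82 to 0.62 (without kidney) or 0.80 to 0.60 (liver, heart wall, muscle) as between-patient CV goes from 30% to 50%. The organ-adjusted value is about 0. With six organs, paired scans at a within-subject CV of 40%, beyond the plan's limit if that limit is a CV, still give 0.85 to 0.86.

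These sizes rest on absorbed dose as a proxy for SUV, lognormal SUVs, the assumed CVs and an illustrative choice of organs. The finding concerns the reference-region coefficient only. Lesions have no fixed organ identity, and no effect on the lesion coefficient has been shown. The consequence is an inflated, hard-to-interpret supporting statistic. It should be corrected before analysis, but it does not by itself undermine the equivalence rule.

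**What to change.** In Section 12:

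1. List the reference regions in advance.
2. Do not use the repeated-measures correlation pooled across different organs as evidence of agreement.
3. For reference regions, report agreement organ by organ with one pair per patient: the cyclotron/generator ratio, within-subject CV and limits of agreement on log SUV, with patient-level confidence intervals. Alternatively, fit one model of log SUV with product and organ as fixed effects and patient and patient-by-organ as random effects.
4. If a pooled correlation is kept, remove organ means first and label it descriptive.
5. State which statistic the 30% criterion applies to.

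The cost is SAP wording and a little more analysis, with no new scans or data. The downside is several organ-specific results in place of one coefficient, with wider intervals and a lower headline value.

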Exploratory Objectives:	
• Investigate repeatability of whole-body ⁶⁸Ga-PSMA-generator Ki Patlak imaging against that of conventional whole-body ⁶⁸Ga-PSMA- SUV imaging in patients with confirmed metastatic prostate adenocarcinoma.

- Evaluate equivalence of whole-body ⁶⁸Ga-PSMA Ki Patlak imaging between the two processes to create ⁶⁸Ga-HBED-PSMA (⁶⁸GA-PSMA-cyclotron vs. ⁶⁸Ga-PSMA-generator)

Endpoints:

The primary endpoint of this study is to prove equivalence between the cyclotron and generator produced radioisotope. To meet this endpoint we will make a direct comparison of the ⁶⁸GA-PSMA-cyclotron vs. ⁶⁸Ga-PSMA-generator scans obtained within 24-48h. We will measure SUVmean and SUVmax of the same Regions of Interest (ROI) in both scans using the PET analysis software we use in our clinical practice. The two scans will be retrieved and the exact same ROIs will be drawn at the same time for the two scans (software offers a copy-paste function so that no discrepancies exist between the two measurements). The SUVmean and SUVmax obtained from both scans for each Region of Interest will then be analyzed to determine the within-subject coefficient of variation value as measured by the Bland Altman analysis.

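### The plan does not say how several ROIs per patient enter the within-subject CV that decides equivalence; if they are pooled unweighted, any confidence interval will be too narrow

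*Combined protocol and SAP*

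**What the plan says.** Section 12 measures SUVmean and SUVmax in the same ROIs on both scans. For the correlation, the ROIs are drawn "for reference regions as well as regions suspicious for metastatic disease", so a patient normally supplies several pairs. The plan knows this needs handling: for the correlation, "we will use the repeated measures correlation coefficient to account for multiple observations per subject".

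The deciding statistic comes next. The SUVs "obtained from both scans for each Region of Interest will then be analyzed to determine the within-subject coefficient of variation value", by Bland-Altman analysis, and the rule follows: "If the agreement between the two scans lies within an acceptable rate (which we consider 30% based on previously published data"), the methods are called equivalent. The synopsis endpoint uses the same construction: the SUVs "will then be analyzed to determine the within-subject coefficient of variation value as measured by the Bland Altman analysis". Neither place gives a rule for combining ROIs, a weight per patient, a cap on lesions or an interval method.

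Two other statements in section 12 bear on this. A mixed-effects framework is named for repeatability, but the functions for "estimating repeatability of measurements with a single grouping factor are all performed in R statistical software" leave the grouping factor unnamed and are not linked to the CV. The section also says the focus will be not on p-values "but rather the estimates of the effect size with its confidence intervals".

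**The concern.** ROIs in one patient are not independent replicates of the product comparison. Each scan has one injection, and the SUV formula in section 3.3 divides every ROI by the same injected activity, so an error in that activity shifts all SUVs of the scan by a common factor. The plan allows further scan-level variation:

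- injected activity will vary (section 3.3);
- the scan ends between 75 and 90 minutes (section 3.1);
- the same scanner is preferred but not required (section 7.1);
- the cyclotron product's specific activity may lie anywhere from 0.1 to 2.0 Ci/µmol (section 12).

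The independent units are therefore the 22 to 30 patients. If every ROI pair counts as one data point, two things follow. The pooled CV leans towards patients with many lesions, and an interval computed from the ROI count claims more information than the trial has. Leaving the unit of analysis open also lets it be chosen after the data are seen.

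**Working it through.** **The plan's own figure.** The only computed design figure is 18.47% power at n = 22 for an odds-ratio equality test. The odds ratio, baseline proportion and sidedness are not given, so it cannot be reproduced. It does not concern the CV.

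**Inputs.** From the documents: 22 or up to 30 patients, and the 30% bound, read here as a bound on the CV. Assumed, because the documents give none: ROIs per patient (m) and the SDs of the log ratio between scans.

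**Model.** For ROI j in patient i the log ratio is d_ij = u_i + e_ij, with SDs s_u (patient) and s_e (ROI).

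- Within-subject CV ≈ √((s_u² + s_e²)/2)
- Within-patient correlation ρ = s_u²/(s_u² + s_e²)
- True SE over ROI-level SE, equal m: √(1 + (m−1)ρ) for the mean log ratio and √(1 + (m−1)ρ²) for the CV. The CV uses squared differences, whose correlation is ρ².

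**Step 1: CV only, equal m.** Simulation with 22 patients, true CV 20% and 3000 runs per cell. Each cell shows the SE ratio and the coverage of a nominal 95% ROI-level interval.

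| ρ | m = 3 | m = 5 | m = 10 |
|---|---|---|---|
| 0 | 0.98, 95% | 1.01, 95% | 0.99, 95% |
| 0.2 | 1.04, 94% | 1.06, 93% | 1.18, 90% |
| 0.5 | 1.25, 88% | 1.40, 84% | 1.79, 73% |
| 0.8 | 1.51, 80% | 1.92, 69% | 2.65, 53% |

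Formula check at m = 10, ρ = 0.5: √(1 + 9 × 0.25) = 1.80, against 1.79 simulated. With 30 patients the ratios are nearly the same. Patient-clustered intervals covered about 91-95%.

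**Step 2: unequal lesion counts.** Geometric lesion counts plus 3 or 6 reference ROIs (about 8 or 11 ROIs per patient), s_u = 0.10-0.20, s_e = 0.15-0.20, 22 or 30 patients. Lowest ρ = 0.01/(0.01 + 0.04) = 0.20; highest ρ = 0.04/(0.04 + 0.0225) = 0.64.

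| Nominal 95% ROI-level interval for | Equal-m formula, m = 8, ρ = 0.20 | Equal-m formula, m = 11, ρ = 0.64 | Simulated coverage, unequal counts |
|---|---|---|---|
| Mean ratio | √2.4 = 1.55, so 79% | √7.4 = 2.72, so 53% | about 46-75% |
| CV | √1.28 = 1.13, so 92% | √5.10 = 2.26, so 61% | about 56-91% |

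Unequal counts lower coverage somewhat below the equal-m values. Patient-level intervals for the mean ratio covered about 95%.

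**Step 3: weighting.** With these counts, the 6 of 30 patients with most lesions supply about 41% (3 reference ROIs) or 35% (6 reference ROIs) of all ROIs, against an equal share of 6/30 = 20%.

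**Step 4: the 30% decision.** The true CV in step 2 runs from √((0.01 + 0.0225)/2) = 0.13 to √((0.04 + 0.04)/2) = 0.20. The pooled CV was essentially unbiased and never exceeded 30%. For scale, in the step 1 cell with m = 10, ρ = 0.5, the ROI-level SE is 0.0095 and the true SE 0.0171. The 95% half-widths are 1.96 × 0.0095 = 0.019 and 1.96 × 0.0171 = 0.034. Both intervals around 20% lie well below 30%.

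**Step 5: does averaging within patient solve it?** Not for the CV. With s_u = 0.10, s_e = 0.20 and 5 ROIs, the CV is √((0.01 + 0.04)/2) = 0.158. From patient means it becomes √((0.01 + 0.04/5)/2) = 0.095. Averaging removes most of the ROI-level variance and makes the 30% rule easier to pass.

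**The case against.** The strongest reply is that the plan nowhere says ROI pairs are pooled or treated as independent. It speaks of a within-subject CV for each ROI, which could mean a separate CV per region, and it names a mixed model and a repeated measures correlation. This stands in part: pooling is inferred from silence. But a per-region reading works only for reference regions that every patient has once. Lesions do not correspond across patients, so several in one patient must still be combined somehow. The mixed model and the correlation are not tied to the CV.

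A second reply is that the plan attaches no interval to the CV and the 30% rule uses none. That is correct. The coverage figures describe an interval that section 12's general commitment to confidence intervals implies but does not define. The larger shortfall concerns the mean product ratio, which the equivalence rule does not use.

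Three stronger readings are tempting and should not be adopted.

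- **The intervals are far too narrow.** This depends on unknown ROI counts and correlation. At ρ = 0.2, CV coverage in step 1 is still 90-94%.
- **A few patients dominate the result.** Under the assumed counts the top fifth supply 35-41% of ROIs: extra weight, but not a majority.
- **The pooling leads to a wrong verdict.** A case can be constructed. Suppose the CV is 20% in patients above the median lesion count and 40% in the rest, with 30 patients and geometric lesion counts (mean 5). The pooled CV then averages 26% and the patient-weighted CV 33%. Reverse the two and they are 36% and 31%, both above 30%. The documents give no sign that the CV varies with lesion burden, nor do they say which weighting is the target.

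**Conclusion.** The concern holds in a limited form. The statistic that decides equivalence has no stated handling of several ROIs per patient, although the same section handles it for the correlation coefficient. If ROI pairs enter unweighted, patients with many lesions get more weight and ROI-level intervals overstate precision. Under the step 2 assumptions, nominal 95% coverage is about 56-91% for the CV and 46-75% for the mean ratio; at low within-patient correlation the CV interval is hardly affected. The ROI counts and variance components are assumptions, since the documents give none. No wrong equivalence decision is shown, because the pooled CV stays below 30% throughout. This is a cheap improvement to make before analysis, not evidence that the planned conclusion would be wrong.

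**What to change.** In section 12 and the synopsis endpoint:

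1. Analyse log SUV separately for reference regions and lesions, for SUVmean and SUVmax. Use product as a fixed effect, with random effects for patient, patient-by-product (scan) and ROI within patient.
2. Derive the within-subject CV from the scan-level plus residual variance components, and the product ratio from the fixed effect. The CV then excludes a systematic product difference, so report both.
3. Give intervals by bootstrap over patients or from the model. With 22 to 30 patients these may still cover slightly below 95%.
4. Do not obtain the CV from log ratios averaged within patient. Patient averaging is acceptable only for the mean product ratio.

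Cost: a paragraph of text and a little more analysis work, with no new data. The reported intervals will be wider.
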